CLINICAL STUDY PROTOCOL

A Multicenter, Randomized, Double-blind, Vehicle-controlled, Parallel-group Comparison Trial to Assess the Efficacy and Safety of 0.3% and 1% OPA-15406 Ointments in Patients With Atopic Dermatitis

NCT Number: 02914548

PRT NO. 271-15-001

PRT Version Date: 29 December 2016 (Version 4)

A Multicenter, Randomized, Double-blind, Vehicle-controlled, Parallel-group Comparison Trial to Assess the Efficacy and Safety of 0.3% and 1% OPA-15406 Ointments in Patients With Atopic Dermatitis
(Phase 2 Trial)

Clinical Protocol

Protocol No.: 271-15-001

(Translated Version)

Confidential

Otsuka Pharmaceutical Co., Ltd.
[name]

Version 4: 29 Dec 2016

Date of Translation: 23 Feb 2017

Statement of Confidentiality

The trial protocol is to be treated as confidential information and is to be made available only to persons involved in the trial. The content of the protocol is not to be disclosed to any third party without the prior written consent of Otsuka Pharmaceutical Co., Ltd., except in the case of its being explained to a candidate trial subject. Disclosure of the results of the trial to academic societies or journals, etc, in part or in whole, will require the prior written approval of Otsuka Pharmaceutical Co., Ltd.

Trial Protocol Synopsis

Name of Investigational Medicinal Product	OPA-15406 Ointment
Trial Title	A Multicenter, Randomized, Double-blind, Vehicle-controlled, Parallel-group Comparison Trial to Assess the Efficacy and Safety of 0.3% and 1% OPA-15406 Ointments in Patients With Atopic Dermatitis (Phase 2 Trial)
Trial Objectives	
Primary Objective: To evaluate Week 4 efficacy of OPA-15406 (0.3% and 1%) compared to the vehicle when administered twice daily for 8 weeks using incidence of success in Investigator's Global Assessment (IGA) as the primary endpoint in patients with atopic dermatitis.
 
Secondary Objective: To evaluate the safety of OPA-15406 (0.3% and 1%) when administered twice daily for 8 weeks in patients with atopic dermatitis.

Phase of Development	
Phase: 2
 
Type of trial: Dose-finding trial

Trial Design	Multicenter, randomized, double-blind, vehicle-controlled, parallel-group comparison trial
Target Population	Atopic dermatitis (AD)
Target Number of Subjects	
180 subjects in total
 
0.3% OPA-15406 group: 60 subjects
 
1% OPA-15406 group: 60 subjects
 
Vehicle group: 60 subjects

Inclusion Criteria	
Subjects who meet all of the following criteria will be eligible for inclusion in this trial.
 
At the screening examination:
 
 1) Sex: Either male or female 2) Hospitalization status: Outpatient 3) Age: 15 to 70 years, inclusive (at time of obtaining informed consent)

	
4) Able to provide written informed consent. For subjects under 20 years of age, written informed consent must be obtained from both the subject and the subject's legal guardian.
 
5) Diagnosis of AD based on the criteria of Hanifin and Rajka¹ (Appendix 1)
 
6) History of AD for at least 3 years
 
At screening and baseline examinations:
 
7) Atopic dermatitis affecting $\geq 5\%$ to $\leq 40\%$ of body surface area (BSA)
 
8) IGA score of 2 (mild) or 3 (moderate)

Exclusion Criteria	
Subjects who fall under any of the following criteria at either the screening or baseline examination will be excluded from the trial:
 
1) Subjects who are pregnant, possibly pregnant, or breastfeeding, who desire to become pregnant or to have their partner become pregnant during the trial period and up until 30 days after the final administration of IMP, or who are unable to either remain abstinent or employ at least two of the specified birth control methods (vasectomy, tubal ligation, vaginal diaphragm, intrauterine device [IUD], birth control pill, condom with spermicide, etc) during the trial period and up until 30 days after the final administration of IMP.
 
2) Subjects who have an AD or contact dermatitis flare-up defined as a sudden intensification of atopic dermatitis, within 28 days prior to the baseline examination
 
3) Subjects who have a concurrent or history of skin disease other than AD (eg, acne, psoriasis, etc) and who are judged inappropriate for assessment of atopic dermatitis in the present trial
 
4) Subjects who have an active viral skin infection (eg, herpes simplex, herpes zoster, chicken pox) or clinically infected AD
 
5) Subjects with a current or history of malignancy within the previous 5 years. However, subjects in whom basal-cell skin carcinoma or squamous-cell skin carcinoma is judged to have been cured at the

	
time of the screening examination can be included in the trial.
 
6) Subjects with a current or history of recurrent bacterial infection resulting in hospitalization or requiring intravenous antibiotic treatment within the past 2 years
 
7) Subjects with a clinically significant complication or history of any of the following disorders that the investigator or subinvestigator judges would prevent safe conduct of the trial or impact efficacy assessments:
 
 • Cardiac disease (eg, rheumatic fever or heart valve replacement) • Endocrinologic disease (eg, severe or uncontrolled diabetes) • Pulmonary disease • Neurologic disease • Psychiatric disease • Hepatic disease (eg, hepatitis B, hepatitis C) • Renal disease • Hematologic disease • Immunologic or immunocompromised disease (eg, lymphoma, acquired immunodeficiency syndrome, Wiskott-Aldrich syndrome, carriers of human immunodeficiency virus [HIV] antibodies) • Other major disease (eg, systemic fungal infection) or other severe uncontrolled condition (eg, drug or alcohol abuse) judged by the investigator or subinvestigator to pose a health risk to the subject or to have the potential to impact trial assessment 
8) Subjects with any of the following hematology or serum chemistry results at screening examination:
 
 • White blood cell count: $\leq 3,000/\mu\text{L}$ or $>14,000/\mu\text{L}$ • Platelets: $\leq 100,000/\mu\text{L}$ • Hemoglobin: $<11\text{ g/dL}$ • Serum creatinine: $\geq 2\text{ mg/dL}$ • Aspartate aminotransferase (AST) (GOT): $>1.5 \times \text{ULN}$ • Alanine aminotransferase (ALT) (GPT): $>1.5 \times \text{ULN}$ • Total bilirubin: $\geq 2.0\text{ mg/dL}$
--	--

	
 • Any other abnormal laboratory test result that the investigator or subinvestigator judges to be a clinically significant abnormality 
9) Subjects who are judged by the investigator or subinvestigator to have clinically significant electrocardiogram (ECG) findings (eg, AV block, prolongation of QRS complex to ≥ 120 msec, or QTcF interval of ≥ 450 msec) at screening examination
 
10) Clinically significant blood pressure or pulse rate findings at screening examination of:
 
 • Age 18 to 70, inclusive: seated resting (≥ 3 minutes) systolic blood pressure of <100 mmHg or ≥ 150 mmHg or diastolic blood pressure of <50 mmHg or ≥ 90 mmHg, or pulse rate of <50 bpm or >100 bpm • Age 15 to 17, inclusive: seated resting ≥ 3 minutes) systolic blood pressure of <95 mmHg or ≥ 140 mmHg or diastolic blood pressure of <50 mmHg or ≥ 90 mmHg, or pulse rate of <50 bpm or >100 bpm 
11) Subjects who are unable to stop using topical corticosteroids, topical immunomodulators, topical retinoids and topical antihistamine from 7 days prior to the baseline examination until the Week 8 assessment. However, corticosteroids categorized as low or medium potency in the “Guidelines of care for the management of atopic dermatitis, Section 2”²
 
12) may be used up until the baseline examination if, in the opinion of the investigator or subinvestigator, their use is necessary, such as when the subjects have been using the corticosteroids prior to providing informed consent to participate in the trial and use of the corticosteroids will be tapered off and stopped during the screening period.
 
13) Subjects who are unable to stop using systemic corticosteroids, systemic immunomodulators, systemic antimetabolites, systemic retinoids and biologics from 28 days prior to the baseline examination until the Week 8 examination. Intra-ocular, intra-nasal, and intra-auricular corticosteroids or inhaled corticosteroids may be considered if, in the opinion of the investigator or subinvestigator, their use will not impact assessment of the affected area.
 
14) Subjects who are unable to stop treatment with

--	--

	
 ultraviolet light A, narrowband ultraviolet B, or ultraviolet light B from 28 days prior to the baseline examination until the Week 8 examination 15) Subjects who are unable to stop using systemic antihistamines, sodium cromoglicate, tranilast, or suplatast tosilate from 7 days prior to the baseline examination until the Week 8 examination 16) Subjects with known hypersensitivity (including history) to any drugs (prescription, OTC, etc) or any ingredient of OPA-15406 ointment 17) Subjects with known plans to receive any of the prohibited concomitant drugs or therapies during the trial period 18) Subjects who have used any other investigational drug within 4 months prior to the baseline examination or who are scheduled to participate in any other clinical trial during the trial period 19) Subjects who have never been treated with a prescription medication for AD or who are satisfied with their current AD treatment regimen 20) Subjects who are judged by the investigator or subinvestigator to be inappropriate to participate in the trial for any other reason
Discontinuation Criteria	
If any of the following events occur during the trial period, the investigator or subinvestigator will withdraw the subject from the trial:
 
 1) Request from the subject or subject's legal guardian to discontinue participation in the trial 2) Discovery that the subject was included in the trial despite violation of the inclusion or exclusion criteria 3) Occurrence of any adverse event that makes it difficult for the subject to continue administration of IMP (including a suspected treatment-related adverse event of skin hypersensitivity on the treatment area) 4) Increase in the total treatment area to more than 40% of BSA 5) Discovery that the subject is pregnant or suspected to be pregnant 6) Judgment by the investigator or subinvestigator that it is necessary to withdraw the subject from the trial
Investigational	Test Product: 0.3% and 1% OPA-15406 ointments

Medicinal Products, Dose and Regimen, and Treatment Period	
Comparator: Vehicle of OPA-15406 ointment
 
Twice daily administration (approximately 12 hours apart between morning and night administration) for 8 weeks

Prohibited Concomitant Drugs, Prohibited Concomitant Therapies	
1) From 28 days prior to the baseline examination until the Week 8 examination, use of the following drugs and therapies is prohibited.
 
 • Systemic corticosteroids, systemic immunomodulators, systemic antimetabolites, systemic retinoids, and biologics Intra-ocular and intra-nasal corticosteroids or inhaled corticosteroids may be considered if, in the opinion of the investigator or subinvestigator, their use will not impact assessment of the affected area. • Ultraviolet light A, narrowband ultraviolet B, and ultraviolet light B 
2) From 7 days prior to the baseline examination until the Week 8 examination, use of the following drugs and therapies is prohibited.
 
 • Topical corticosteroids, topical immunomodulators, topical retinoids, and topical anti-histamine. • Corticosteroids categorized as low or medium potency in the “Guidelines of care for management of atopic dermatitis, Section 2” • may be used up until the baseline examination (up until the Week 8 examination on the face, neck, and head) if, in the opinion of the investigator or subinvestigator, their use is necessary, such as when the subjects have been using the corticosteroids prior to providing informed consent to participate in the trial and use of the corticosteroids will be tapered off and stopped during the screening period. • Systemic antihistamines, sodium cromoglicate, tranilast, suplatast tosilate 
3) From the baseline examination until the Week 8 examination, use of the following drugs and products on the treatment area is prohibited.
 
 • All topical drugs (including ethical drugs, over-the-counter products, herbal medicine, quasi-drugs, and cosmetic products) However, if cosmetic products were being used on the face, neck, and head prior to obtaining consent, their use may be continued

	only if the same products are used at the same frequency.
Variables	
Efficacy Endpoints:
 
Primary Outcome Variable:
 
Incidence of success in IGA at Week 4: Percentage of subjects in whom IGA score is 0 (clear) or 1 (almost clear) and improved at least 2 grades from baseline
 
Secondary Outcome Variables:
 
 1) Incidence of success in IGA at Week 1 and Week 8 2) Change from baseline in IGA at Week 1, Week 4, and Week 8 3) Change from baseline in the total score of Eczema Area and Severity Index (EASI) and each symptom score at Week 1, Week 4, and Week 8 4) Change from baseline in Visual Analogue Scale (VAS) for pruritus at Week 1, Week 4, and Week 8 5) Change from baseline in Verbal Rating Scale (VRS) for pruritus up to Day 7 6) Change from baseline in the total score of Dermatology Life Quality Index (DLQI) at Week 1, Week 4, and Week 8 7) Change from baseline in the total score of Patient-Oriented Eczema Measure (POEM) at Week 1, Week 4, and Week 8 8) Change from baseline in the total affected BSA (%) at Week 1, Week 4, and Week 8 9) Time to response in IGA and VRS 
Safety Endpoints:
 
Adverse events, physical examination, vital signs (including body weight), clinical laboratory values, and 12-lead ECG
 
Pharmacokinetics:
 
 1) Plasma trough concentrations of OPA-15406 (prior to IMP administration at Week 1, Week 4, and Week 8 of IMP administration; all subjects) 2) Plasma concentrations of OPA-15406 (prior to IMP

	
administration and 2 hours, 4 hours, and 8 hours postdose on Day 1 and at Week 4; specific trial sites; target of 6 subjects from each group)
 
• Pharmacokinetic parameters of OPA-15406: C_{max}, t_{max}, and AUC_{0-8h} on Day 1 and at Week 4 of IMP administration• Accumulation of OPA-15406: Ratio of C_{max} and AUC_{0-8h} at Week 4 and on Day 1 of IMP administration
Scheduled Duration of the Trial	21 Jul 2016 to 31 Jul 2017

<Schedule of Observations/Examinations/Evaluations>

Evaluation	Screening period (2-30 days)	Assessment period (8 weeks)							Post-treatment observation period (2 weeks)
		Baseline examination	Week 1 examination ^a	Week 2 examination ^b	Week 4 examination ^b	Week 6 examination ^b	Week 8 examination ^b	Withdrawal examination ^d	
Informed consent	○								
Inclusion and exclusion criteria	○	○							
Subject demographics	○								
Physical examination	○	○	○	○	○	○	○	○ ^e	○
Vital signs (including body weight)	○	○	○	○	○	○	○	○ ^e	
12-lead EC ^f G	○	○ ^g			○		○	○ ^e	
Clinical laboratory tests	○	○ ^g			○		○	○ ^e	
Pregnancy test ^h	○	○ ^g			○		○	○ ^e	
IGA	○	○	○	○	○	○	○		
EASI		○	○	○	○	○	○		
VAS for pruritus		○	○	○	○	○	○		
VRS for pruritus		○ ⁱ	↔	○					
DLQI		○	○	○	○	○	○		
POEM		○	○	○	○	○	○		

<Schedule of Observations/Examinations/Evaluations, Continued>

Evaluation	Screening period (2–30 days)	Assessment period (8 weeks)							Post-treatment observation period (2 weeks)
		Baseline examination	Week 1 examination ^a	Week 2 examination ^b	Week 4 examination ^b	Week 6 examination ^b	Week 8 examination ^b	Withdrawal examination	
Affected BSA	○	○	○	○	○	○	○	○	
Treatment area		○	○	○	○	○		○	
Blood sampling for plasma drug concentration measurement			○ ^J		○ ^J		○ ^K		
Administration diary		○ ^I	←	→			○		
Severity of AD		○							
Status of IMP administration			○	○	○	○	○		
Prescription and collection of IMP		○ ^m	○ ⁿ	○	○	○	○ ^o	○ ⁿ	
Adverse events		←	→						
Concomitant medications and therapies		←	→						
Patch test ^p		←	→						

AD = atopic dermatitis; DLQI = Dermatology Life Quality Index; EASI = Eczema Area and Severity Index; IGA = Investigator's Global Assessment; POEM = Patient-Oriented Eczema Measure; VAS = Visual Analogue Scale; VRS = Verbal Rating Scale.

^a Acceptable window of ± 2 days

^b Acceptable window of ± 3 days

^c Acceptable window of ± 7 days

^d Withdrawal examination should be conducted as much as possible.

^e May be conducted, as necessary.

^f Should be conducted prior to blood sampling, as much as possible.

^g Results of the screening examination should be used when the baseline examination is planned within 7 days of the screening examination.

^h Should be conducted only for women with childbearing potential.

ⁱ Should be evaluated during the baseline examination, 4 ± 2 hours, 8 ± 2 hours, and 12 ± 2 hours (if possible) after the first IMP administration, and then twice daily from the next day (before IMP administration in the morning and at night) until the morning of the Week 1 examination (without IMP application) (up to the morning of Day 7 at the latest).

^j On the day of blood sampling, the first IMP application should not be done until after blood sampling when visiting the trial site.

^k On the day of examination, the subjects should not administer the IMP.

^l The subjects should keep a diary every day from the baseline examination to the Week 8 examination (withdrawal examination).

^m Only IMP prescription.

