3.3.3 Pharmacokinetics

Plasma trough concentration of OPA-15406 (trough concentration at Week 1, Week 4, and Week 8)

- 1) Plasma trough concentrations of OPA-15406 (prior to IMP administration at Week 1, Week 4, and Week 8 of IMP administration; all subjects)
- 2) Plasma concentration of OPA-15406 (prior to IMP administration and 2 hours, 4 hours, and 8 hours postdose on Day 1 and at Week 4; specific sites [target of 6 subjects from each group])
 - Pharmacokinetic parameters of OPA-15406: C_{max} , t_{max} , AUC_{0-8h} on Day 1 and at Week 4 of IMP administration
 - Accumulation of OPA-15406: Ratio of C_{max} and AUC_{0-8h} at Week 4 and on Day 1 of IMP administration

[Rationale for variable selection]

[Efficacy]

The primary variable of IGA is an indicator to assess the severity of AD and also a reliable indicator to determine the efficacy of the IMP; therefore, IGA has been established as the primary efficacy endpoint. IGA is evaluated based on the severity of overall symptoms (erythema, infiltration, papules, effusion, and scab formation) at treatment area and does not include other factors (eg, excoriation, symptoms of lichenification, severity of each part, subjective symptoms, affected BSA). Therefore, EASI, VAS and VRS for pruritus, DLQI, POEM, and affected BSA have been established as the secondary variables to evaluate the efficacy from multiple

points of view.
[Safety]
To appropriately assess the safety of this product.
[Pharmacokinetics]
To determine pharmacokinetics of OPA-15406 and the internal exposure to OPA-15406 in Japanese AD patients.

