6.2 Treatment Area

The treatment area with the IMP is defined as follows.

- The treatment area selected at baseline examination will be affected area determined at baseline examination (see [7.2.1.7 “Affected BSA”](#)).
- After the baseline examination, when the affected area has expanded or a new affected area is detected, the expanded or newly affected area will also be included in the treatment area.
- Even when the affected area is relieved, the IMP administration should be continued there as the treatment area.

The investigator or subinvestigator will instruct the subject regarding the method of administration by specifying the treatment area (%) and the amount of administration (g) for each treatment area using the human body drawing (Appendix 5), and will give the human body drawing (copy) to the subject or the subject's legal guardian. The investigator or subinvestigator will record the treatment area (%) of the 4 body regions (face, neck, and head; upper limbs; trunk; and lower limbs) in the source document and case report form (CRF).

The method of IMP administration is specified in the separate procedure for IMP administration.

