6.3 Prior and Concomitant Treatment

6.3.1 Prohibited Concomitant Drugs and Therapies

- 1) From 28 days prior to the baseline examination until the Week 8 examination, use of the following drugs and therapies is prohibited
 - Systemic corticosteroids, systemic immunomodulators, systemic antimetabolites, systemic retinoids, biologics
Intra-ocular, intra-nasal, and intra-auricular corticosteroids or inhaled corticosteroids may be considered if, in the opinion of the investigator or subinvestigator, their use will not impact assessment of the affected area.
 - Ultraviolet light A, narrowband ultraviolet B, ultraviolet light B
- 2) From 7 days prior to the baseline examination until the Week 8 examination, use of the following drugs and therapies is prohibited.
 - Topical corticosteroids, topical immunomodulators, topical retinoids, and topical antihistamine.
However, corticosteroids categorized as low or medium potency in the “Guidelines of care for management of atopic dermatitis, Section 2”² may be used up until the baseline examination if, in the opinion of the investigator or subinvestigator, their use is necessary, such as when the subjects have been using the corticosteroids prior to providing informed consent to participate in the trial and use of the corticosteroids will be tapered off and stopped during the screening period.
 - Systemic antihistamines, sodium cromoglicate, tranilast, suplatast tosilate
- 3) From the baseline examination until the Week 8 examination, use of the following drugs and products on the treatment area is prohibited.
 - All topical drugs (including ethical drugs, over-the-counter products, herbal medicine, quasi-drugs, and cosmetic products)
However, if cosmetic products were being used on the face, neck, and head prior to obtaining consent, their use may be continued only if the same products are used at the same frequency.

All other drugs and therapies not specified in the prohibited concomitant drugs and therapies are allowed to be used; however, any regimen or dose change or use of a new drug or therapy should be avoided as much as possible between the screening examination and the Week 8 examination. If any drug other than the IMP is used between 30 days before the screening examination and the Week 8 examination, the name of the drug, purpose of use, amount per dose, dose frequency, route of administration, and dates of start and end of administration will be recorded in the source

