document and CRF, regardless of it being prohibited or allowed for concomitant use. If any concomitant therapy is given between 30 days before the screening examination and the Week 8 examination, regardless of it being prohibited or allowed for concomitant use, the name of the therapy, purpose of use, and the dates of the start and end of the therapy will be recorded in the source document and CRF.

[Rationale for prohibited concomitant drugs and therapies]

Due to a possible impact on the efficacy and safety assessments of the IMP.

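### The protocol gives two current rules on low or medium potency topical corticosteroids on the face, neck and head after baseline, and the SAP has no rule for such use in the primary endpoint

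*Protocol*

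**What the plan says.** Four places in the current protocol deal with low or medium potency topical corticosteroids around baseline.

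- **Synopsis, Prohibited Concomitant Drugs, item 2:** they "may be used up until the baseline examination (up until the Week 8 examination on the face, neck, and head", with a closing condition that their use be necessary.
- **Section 6.3.1, item 2:** they "may be used up until the baseline examination if, in the opinion of the investigator or subinvestigator, their use is necessary". There is no face, neck and head extension.
- **Section 5.3, exclusion criterion 11, and its copy in the synopsis:** the same wording as Section 6.3.1. Both also exclude subjects who cannot stay off topical corticosteroids through Week 8.

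Item 3, present in both the synopsis and Section 6.3.1, adds: "From the baseline examination until the Week 8 examination, use of the following drugs and products on the treatment area is prohibited". It covers all topical drugs, and its only face, neck and head exception is for cosmetic products already in use.

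Section 6.2 makes affected skin the treatment area, and if lesions spread or appear, "the expanded or newly affected area will also be included in the treatment area". The rationale under Section 3.3.3 says that "IGA is evaluated based on the severity of overall symptoms (erythema, infiltration, papules, effusion, and scab formation) at treatment area".

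On the analysis side, SAP 6.3.1 turns only a missing IGA into non-response. SAP 6.4 selects efficacy data by the dates of study drug, and SAP 9 analyses efficacy in the full analysis set. Major deviations and concomitant medications are tabulated (SAP 7.3 and 8.3).

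**The concern.** Sites hold two current rules on an active topical therapy between baseline and Week 8. Whether a given use is allowed or is a deviation depends on which page the site follows, so deviation counts will not mean the same thing across sites.

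If a site takes the synopsis parenthesis as overriding item 3, a steroid could be applied to facial or neck skin that is also being treated and scored. An IGA of 0 or 1 with a two-grade fall would then count as a success of the assigned ointment. None of the three sensitivity analyses in SAP 6.3.1 (LOCF, observed cases, and 0 or 1 without the two-grade requirement) looks at other therapy, so the reported results could not show whether this had happened.

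**Working it through.** **1. The texts side by side**

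| Place | Allowance ends, face/neck/head | Allowance ends, elsewhere |
|---|---|---|
| Synopsis, prohibited drugs, item 2 | Week 8 | Baseline |
| Section 6.3.1, item 2 | Baseline | Baseline |
| Section 5.3, criterion 11 | Baseline | Baseline |
| Synopsis, exclusion criteria | Baseline | Baseline |

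The synopsis disagrees with the body and with its own exclusion criteria. It also sits badly within one sentence: the example given for the allowance is a steroid withdrawn during screening, which does not fit use to Week 8. A complete parenthesis with its own time limit and body regions is not an extraction fault.

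**2. Does item 3 remove the conflict?** Only in part. Item 2 of Section 6.3.1 is not limited to the treatment area. Use on the face outside that area is therefore allowed by the synopsis and prohibited by Section 6.3.1, whatever item 3 says. For skin inside the treatment area, items 2 and 3 read together bar the steroid under both versions. Scored skin is exposed only on the reading that the parenthesis is an exception to item 3.

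**3. How would the SAP handle it on that reading?** The IGA is observed, so it is scored as it stands. Two existing controls are partial. Criterion 16 excludes subjects with known plans to use prohibited therapy, and Section 9.2 withdraws subjects found to have violated eligibility. Under SAP 6.4, however, an IGA at discontinuation on days 22 to 35 is still assigned to Week 4, provided it is within 7 days of the last study drug.

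**4. How sensitive is the primary test to a few extra responders?** The plan gives no figure on this point, so there is none to reproduce. The following is an illustration with assumed additions.

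*Inputs.* 60 per arm; success rates 2.70% (vehicle) and 20.93% (1%) from Section 11.5 and SAP 12.2; 14.63% (0.3%) from Section 1.2.2.4. Expected successes: 60 × 0.0270 = 1.6, 60 × 0.1463 = 8.8, 60 × 0.2093 = 12.6.

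*Test.* Cochran-Mantel-Haenszel without continuity correction, two-sided 5%, one stratum. With *a* active and *b* vehicle successes and *m* = *a* + *b*, the statistic is (*a* − *m*/2)² / V, with V = *m*(120 − *m*)/(4 × 119), compared with 3.84.

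- *b* = 0: *a* = 3 gives 2.25/0.737 = 3.05; *a* = 4 gives 4/0.975 = 4.10. Four are needed.
- *b* = 1: *a* = 6 gives 6.25/1.662 = 3.76; *a* = 7 gives 9/1.882 = 4.78. Seven are needed.

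One vehicle success thus raises the requirement from 4 to 7.

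*Method.* Exact binomial enumeration, with one or two successes added as fixed counts on top of the binomial draw. The 0.3% result requires both tests to be significant, sharing the vehicle arm, as the closed procedure does.

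| Added successes | 1% vs vehicle, +1 / +2 | Gated 0.3% vs vehicle, +1 / +2 |
|---|---|---|
| None | 0.923 | 0.659 |
| Vehicle only | 0.837 / 0.705 | 0.455 / 0.258 |
| All arms | 0.893 / 0.859 | 0.579 / 0.489 |
| Active arms only | 0.954 / 0.974 | 0.761 / 0.843 |

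*Stratified check.* The planned test is stratified by baseline IGA. Simulation (400,000 trials per setting) used mild:moderate splits of 18:42, 30:30 and 42:18 per arm, mild success rates of 1, 0.5 and 0.25 times the moderate rate, and additions in the moderate stratum. With none added it gives 0.924–0.941 for 1% and 0.663–0.693 for gated 0.3%. No scenario moves by more than about 7 points, and each keeps its direction.

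**The case against.** The strongest reply is that the endpoint link is weak on the documents' own text. Item 3 is the same in both places, states its own head and neck exception (cosmetics only), and covers all affected skin, including new and resolved lesions. Followed as written, it keeps steroid off scored skin under either version of item 2, leaving a conflict only over head and neck skin outside the treatment area. This stands, and it is why the endpoint risk is stated as conditional. It does not settle the matter: if item 3 always governed, the Week 8 parenthesis would have little left to permit, so a site could reasonably read it as an exception.

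Second, the power figures do not measure this defect. The added successes are assumed, and any cause of one or two extra responders would do the same at a 2.70% vehicle rate. The vehicle-only scenario is also not the natural expectation under blinding with allocation balanced within site. The convention matters somewhat: raising the vehicle rate by k/60 instead gives 82% / 69% rather than 84% / 71% for 1%, and 30% rather than 26% for gated 0.3% with two added. All of this is accepted; the table shows fragility, not an expected bias.

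Third, application site is not among the listed case report form fields, so the proposed sensitivity analysis cannot separate on-area from off-area use. It would also score use as non-response even if the reconciled rule permits it. Both limits stand, which is why the analysis is supportive only.

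Finally, the protocol is a translation, and whether the source text has the same mismatch cannot be checked here.

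**Conclusion.** The inconsistency is certain: one current passage extends the allowance to Week 8 on the face, neck and head, three end it at baseline, and no order of precedence is given. It concerns active therapy in the period leading to the primary endpoint and should be fixed.

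Any effect on the Week 4 result rests on three conditions: a site lets the parenthesis override item 3, the steroid is used on scored skin, and the overall IGA reaches 0 or 1 with a two-grade fall that would not otherwise have occurred. The documents give no rate of use, no steroid effect and no imbalance between arms, so neither the size nor the direction of a bias can be stated. What can be said is that, with fewer than two vehicle successes expected, the primary test and especially the gated 0.3% test have little tolerance for even one or two misattributed responses.

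**What to change.** 1. Reconcile the synopsis (prohibited drugs item 2 and the exclusion criterion), Section 5.3 criterion 11 and Section 6.3.1 item 2 so that there is one rule, make its relation to item 3 explicit, and notify sites. Which rule to adopt is a clinical decision on which no view is given here.

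2. Add one supportive sensitivity analysis of the primary endpoint to SAP 6.3.1 and 9.1.1. A subject is a non-responder if a topical (skin) corticosteroid, or other prohibited therapy given for atopic dermatitis, is recorded with use after the day of the baseline examination and up to the IGA used for Week 4. Do not count use ending on or before the baseline day, or the non-skin corticosteroids that Section 6.3.1 item 1 treats separately ("Intra-ocular, intra-nasal, and intra-auricular corticosteroids or inhaled corticosteroids may be considered"). State that the analysis applies whichever rule is adopted, and that it may reclassify subjects who used a steroid away from the scored area.

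The cost is a wording correction, a site notice and one extra analysis, which the SAP can still take in before database lock. No new data are needed. For drugs, Section 6.3.1 already requires "the name of the drug, purpose of use, amount per dose, dose frequency, route of administration, and dates of start and end of administration", whether the drug is prohibited or allowed; for therapies, "the name of the therapy, purpose of use, and the dates of the start and end of the therapy will be recorded". The primary analysis is unchanged. The downside is possible reclassification of off-area users, in number unknown, in the sensitivity analysis only.
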